13.3 Discontinuation Criteria

A subject may be discontinued from the study or study drug for any of the following reasons:

- Withdrawal of consent;
- Investigator or Sponsor decision that withdrawal is in the subject's best interest;
- Deterioration of the clinical condition or delayed response requiring, in the opinion of the investigator, alternative therapy.
- Occurrence of an AE that, in the opinion of the investigator, warrants discontinuation of the subject from the study drug;
- Pregnancy;

• Lost to follow up (every attempt should be made to contact the subject).

The reason for a subject's discontinuation of treatment or withdrawal from the study will be clearly documented in the source documents and on the electronic case report form (eCRF). All EoT procedures should be performed for subjects who discontinue from study treatment before the EoT visit.

13.4 Replacement of Dropouts

Subjects who discontinue early from treatment will not be replaced.

14.0 Study Treatments

14.1 Study Treatment Groups

This is an open-label, single-arm study. All enrolled subjects will receive an initial oral loading dose of 750 mg of SCY-078 (3 tablets of 250 mg) BID during the first 2 days of treatment and then subsequent oral doses of 750 mg QD for up to 90 days.

For subjects who are unable to take oral medications, tablets may be crushed and administered with approximately 8 oz./240 mL of water via an NG or PEG tube. The tube should be closed at least one hour before drug administration and be flushed with approximately 8 oz./240 mL of water before and after drug administration.

Oral treatment may be given on an inpatient or outpatient basis, as needed, and for as long as is clinically indicated, at the investigator's discretion, but in no event for more than a total of 90 days of antifungal treatment.

14.2 Dietary Requirements

Oral study drug should be taken with approximately 8 oz./240 mL of water. For subjects on continuous feeding via an NG or PEG tube, the drug should be crushed and administered with approximately 8 oz./240 mL of water. The tube should be closed at least one hour before drug administration and should be flushed with approximately 8 oz./240 mL of water before and after drug administration.

Subjects who are not hospitalized or are hospitalized and then discharged will be instructed to take the study medication in the morning upon arising and in the evening, approximately 12 hours apart (for Day 1 and Day 2). For Day 3 onwards, subjects will be instructed to take the study medication in the morning upon arising only. Subjects must take the study drug with approximately 8 oz./240 mL of water in all cases. Nutraceuticals and foods that are known CYP3A inhibitors,

such as grapefruit juice, blood oranges and mulberry juice should not be consumed during the study (see Section 23.1 [Appendix A]).

14.3 Study Drugs

The study drug, SCY-078 250-mg tablets, will be provided by the Sponsor.

14.3.1 SCY-078 Description

Study Drug Identifier:	SCY-078
Empirical Formula:	C ₅₀ H ₇₅ N ₅ O ₁₁ (citrate salt)
Molecular Weight:	922.18 (citrate salt)
Physical Description:	White to off-white solid
Chemical Name:	(1S,4aR,6aS,7R,8R,10aR,10bR,12aR,14R,15R)-15-[[(2R)-2-amino- 2,3,3-trimethylbutyl]oxy]-8-[(1R)-1,2-dimethylpropyl]-14-[5-(4- pyridinyl)-1H-1,2,4-triazol-1-yl]-1,6,6a,7,8,9,10,10a,10b,11,12,12a-

pyridinyl)-1H-1,2,4-triazol-1-yl]-1,6,6a,7,8,9,10,10a,10b,11,12,1 dodecahydro-1,6a,8,10a-tetramethyl-4H-1,4a-propano-2Hphenanthro[1,2-c]pyran-7-carboxylic acid, citrate salt]

Figure 2Chemical Structure of SCY-078 Citrate

14.3.2 Formulation, Packaging and Labelling

SCY-078 citrate drug product for oral administration will be supplied as a tablet containing 250 mg of SCY-078 active ingredient on a free-base basis. In addition to the active ingredient, the tablet formulation also contains silicified microcrystalline cellulose, crospovidone, mannitol, colloidal silicon dioxide, magnesium stearate (non-bovine) and butylated hydroxyanisole.

Study drug supplies will be packaged in bottles. Labels on the bottles of SCY-078 will include the following information:

- Sponsor information
- Protocol number
- Protocol visit number
- Place to write the subject number
- Route of administration
- Lot number
- Product name and potency
- Contents, e.g. number of tablet count per bottle
- Storage conditions
- Name of manufacturer and date of manufacture
- Caution statement: "Caution: New Drug Limited by Federal (United States) Law to Investigational Use Only"

14.3.3 Storage and Stability

The pharmacist or appropriate designee at each clinical research site will be responsible for the study drug. For long-term storage at the site, study drug supplies provided in bottles must be kept in a secure area (e.g., locked cabinet) and stored at room temperature, between 15°C and 30°C.

The site will be required to keep a temperature log to establish a record of compliance with these storage conditions. All study drug will be kept in a secure cabinet or room with access restricted to necessary clinic personnel.

14.4 Drug Accountability

The investigator or designee will inventory and acknowledge receipt of all shipments of the study drug. Drug accountability logs will be used to maintain accurate records of receipt, dispensing, administration to each subject and return of drug. A study monitor will periodically check the supplies of investigational products held by the site to verify accountability of all study drugs. At the conclusion of the study, after final drug accountability has been completed by the monitor, all unused study drug and all medication containers will be returned to the Sponsor or destroyed on site if the site has procedures in place for study drug destruction.

Drug supplies will be maintained in a secure, limited-access storage area under the recommended storage conditions (see Section 14.3.3).

The study drug supplied for this study is only for use in subjects properly consented and enrolled under this protocol.

This is an open-label study. A study site designee (e.g. pharmacist, study nurse/coordinator) will:

- Record the treatment in the appropriate drug accountability log
- Count the number of tablets per bottle before dispensing to the subject
- Report and document any study medication issues such as crushed or broken tablets
 - All product quality complaints should be reported to the Sponsor
- Collect and count the number of tablets remaining at the EoT visit
- Review subject diary and tablet count, record any unused or remaining drug in the drug accountability log and eCRF, and note any discrepancies and reason for discrepancies

14.5 Subject Compliance with Study Drug Dosing

Subjects who are not hospitalized and subjects who are discharged from the hospital will be instructed to have the study medication (including empty bottles/units) with them at each visit. Compliance will be assessed based on remaining study drug as compared to what should have been taken and the subject diary where the subject will enter the details of dosing. Details of treatment including any missing dose will be recorded in the eCRF. Sites are encouraged to contact the medical monitor or Sponsor for concerns of compliance with the treatment regimen, especially for subjects who miss doses due to problems with tolerability.

15.0 Non-Study Treatments

15.1 Prior and Concomitant Medications

All medications (including prescription and OTC medications, supplements, and herbal products) taken from 28 days before Screening/Treatment Day 1 through the EoT will be recorded on the eCRF. Only the use of antifungal medications, antibiotics for any reason or medications to treat an AE will be recorded after EoT and through the Week 6 Follow-up visit. Start and stop times of concomitant medications taken during antifungal therapy will be recorded on the eCRF. Subjects will also record any new concomitant medications taken between visits in the subject diary.

Certain concomitant medications must be administered with caution or close monitoring as described in Section 15.2 and Section 15.3.

15.2 Prohibited Medications

Medications specifically not permitted prior to the study and through the Week-6 Follow-up visit include the following:

- Other investigational drug(s)
- Other antifungals
- Select strong CYP3A4/5 inhibitors, select moderate CYP3A4/5 inhibitors, select CYP3A4/5 inducers, and select P-gp substrates.

A detailed list of prohibited medications and timeframes is provided in Section 23.1 (Appendix A).

15.3 Medications to be Administered with Caution and Monitored as Appropriate

The following medications must be administered with caution and must be monitored as appropriate:

- Select moderate CYP3A4/5 inhibitors
- Select CYP3A4 substrates, including but not limited to sirolimus, tacrolimus and warfarin

A detailed list of medications to be administered with caution is provided in Section 23.1 (Appendix A).

15.4 Study Restrictions

There are no additional study restrictions other than those described in Sections 13.2 (Exclusion Criteria), Section 14.2 (Dietary Requirements) and Section 15.2 (Prohibited Medications).

16.0 Study Procedures

The following sections provide a description of the individual study procedures to be performed during the conduct of the study. Detailed schedules of study assessments are provided in the Schedule of Visits and Procedures in Table 1.

16.1 Informed Consent

Every study subject (or the subject's legal representative) must provide written informed consent at Screening/Treatment Day 1, prior to participating in any Screening evaluations or any other study activities (see Section 21.3).

16.2 Inclusion and Exclusion Criteria

All inclusion and exclusion criteria will be reviewed at Screening/Treatment Day 1 (prior to study treatment) to ensure that the subject qualifies for the trial.

16.3 Subject Enrollment and Assignment of Subject Number

At Screening/Treatment Day 1, all subjects who have signed an ICF will receive an 8-digit subject identification (ID) number (prior to study treatment) that will be composed of a 3-digit study number (305) and a 2-digit site number followed by a 3-digit sequentially assigned subject number starting at 001. Subject numbers will be sequentially assigned by the database upon entry by the site. For instance, if site 01 enters the first subject in the database, the subject ID will be 305-01-001. The second subject entered in the database will get the subject number 002 as entered by any site, so that if site 02 enters the second subject, the subject ID will be 305-02-002. This number will be unique to each subject and will be used to identify the subject throughout the study.

Subjects who are screen failures or who are not eligible for enrolment will be recorded as such in the subject screening log. The subject numbers assigned to eligible subjects will be recorded in the eCRF. Only one subject number will be assigned to each eligible subject.

For subjects who signed an ICF (i.e., are assigned a subject number) but were NOT treated because they did not meet all of the inclusion/exclusion criteria, the Screening/Treatment Day 1 visit pages of the eCRF will be completed. The criteria that were not met for enrolment will be documented in the eCRF.

All eligible subjects must be approved by the Sponsor for enrollment.

16.4 Medical History and Demographics

During the Screening/Treatment Day 1 visit (prior to study treatment), a complete medical history for the prior year will be recorded for each subject. The medical history will include previous and current medical diagnoses, as well as major surgical procedures. Subject demographics such as age, sex, race and ethnicity will also be collected.

16.5 General Physical Examination

A general physical exam will be done at Screening/Treatment Day 1 (prior to study treatment), at EoT and at the Week-6 Follow-up visit. The physical examination will include an abbreviated assessment of general appearance, skin, eyes, heart, chest and abdomen.

16.6 Vital Signs

Vital signs, including blood pressure (systolic and diastolic), heart rate, respiratory rate and body temperature will be measured at Screening/Treatment Day 1 (prior to study treatment), at EoT and at unscheduled visits, if applicable.

16.7 Twelve-Lead Electrocardiogram

A 12-lead ECG will be obtained and evaluated locally by a physician for the presence of abnormalities at Screening/Treatment Day 1 (prior to study treatment), at EoT and at unscheduled visits, if applicable.

Heart rate, PR interval, QRS, QT and QTcF values will be recorded in the eCRF. Any clinically relevant abnormality will be recorded as AE accordingly and will be followed up to resolution/satisfaction.

16.8 Pregnancy Test

A serum pregnancy test will be performed at Screening/Treatment Day 1 (prior to study treatment) and at EoT by the local laboratory for all female subjects of childbearing potential.

16.9 Targeted Physical Examination, Including Clinical Evaluation of Signs and Symptoms of Infection

A targeted examination of the fungal infection site, including the signs and symptoms of the fungal disease, will be conducted at Screening/Treatment Day 1 (prior to study treatment), Treatment Days 3 to 5, Treatment Days 7 to 10, every 14 days thereafter up to EoT, at EoT, and at the Week 6 Follow-up.

The signs and symptoms of the fungal disease include, but are not limited to, the following:

- Fever, defined as oral temperature ≥38.3°C (≥101°F) on one occasion or >37.8°C (>100°F) on two measurements at least 4 hours apart
- Clinically significant hypothermia <36°C (<96.8°F)
- Hypotension (systolic blood pressure <90 mmHg or a >30 mmHg decrease below normal baseline)
- Tachycardia

Subjects who are discharged from the hospital during SCY-078 therapy will record signs and symptoms daily on subject diaries and the signs and symptoms will also be assessed by the site staff at the study visits. The site will assess whether the signs and symptoms recorded on the subject diary are related to the *C. auris* infection.

16.10 Mycological Testing

Blood cultures: Two sets of blood cultures will be collected at Screening/Treatment Day 1 (prior to study treatment) and repeated daily or every other day until blood cultures are negative for at least 48 hours (if it is only possible to obtain 1 set of blood cultures, a reason should be documented). Blood should be drawn peripherally [directly from a vein]; however, if this is not possible, blood may be drawn from a central IV catheter. Follow-up cultures will be performed as clinically indicated.

Non-blood cultures: A documented culture positive for *C. auris* of a sample obtained within the last 7 days must be available at Screening/Treatment Day 1 (prior to study treatment). Follow-up cultures from subjects who have non-blood *Candida auris* infections should be performed as clinically indicated.

The study site's local microbiology laboratory will perform identification and *in vitro* susceptibility testing as per their local standards. The investigator should ensure that all *Candida auris* isolates obtained from all cultures performed during the study period are sent to the central microbiology laboratory, as described in the laboratory manual.

Further evaluation to identify the potential mechanism of resistance may be performed. Isolates may be maintained in a repository for potential future use, for subjects that provide consent for future use.

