10.0 Study Objectives

10.1 Primary Objectives

• To evaluate the efficacy of SCY-078 as determined by a Data Monitoring Committee (DMC) by assessing global success (composite assessment of clinical and mycological success) at End of Treatment (EoT).

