11.0 Study Endpoints

11.1 Primary Endpoints

• Efficacy as measured by the percentage of subjects with global success (complete or partial global response) at EoT as determined by the DMC

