16.11 Imaging

Imaging scans (e.g., X-ray, ultrasound, computed tomography, magnetic resonance imaging) should be performed for the assessment of infection in subjects with non-blood sites of *Candida* infection. The results of these studies should be documented on the eCRF.

For subjects with fungal diseases where the assessment of outcome is based on imaging, imaging scans must be available at Screening/Treatment Day 1 (prior to study treatment) and performed at EoT. Additional images should be obtained if clinically indicated.

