20.7 Efficacy

20.7.1 Efficacy Assessments

20.7.1.1 Clinical, Mycological and Global Outcomes

Efficacy will be assessed primarily in terms of global success (defined as a complete or partial global (clinical and mycological) response) at EoT as determined by the DMC. Complete global response, partial global response, stable disease and progressive disease at EoT as determined by the DMC will be assessed as exploratory endpoints. Global success, clinical success and mycological success at EoT as determined by the investigator will also be assessed as exploratory endpoints.

Global Outcome

Global outcome will be scored as global success (complete global response or partial global response) or global failure (stable disease or progressive disease)

Global success: Global success is defined as a complete global response or a partial global response

- Complete global response is defined as a complete clinical response (the resolution of all clinical signs and symptoms and/or radiological abnormalities from baseline attributable to the *Candida auris* infection) and a mycological response (mycological clearance (direct and/or negative cultures [when obtainable] and/or normal serological results [when appropriate])
- Partial global response is defined as a partial clinical response (major improvement of all clinical signs and symptoms and/or radiological abnormalities from baseline attributable to the *Candida auris* infection) and a mycological response (mycological clearance (direct and/or negative cultures [when obtainable] and/or normal serological results [when appropriate])

Global failure: Global failure is defined as either stable disease and/or progressive disease

- Stable disease is defined as minor or no clinical improvement but without deterioration and/or unchanged serological response.
- Progressive disease is defined as clinical deterioration necessitating alternative antifungal therapy or resulting in death, and/or worsened serological response, and/or persistence of fungal infection on the basis of culture, microscopic evaluation, or histopathological testing.

Clinical Outcome

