Clinical success: clinical success is defined as a complete clinical response (the resolution of all clinical signs and symptoms and/or radiological abnormalities from baseline attributable to the *Candida auris* infection) or a partial clinical response (major improvement of all clinical signs and symptoms and/or radiological abnormalities from baseline attributable to the *Candida* auris infection).

Mycological Outcome

Mycological success: mycological success is defined as a mycological response (mycological clearance (direct and/or negative cultures [when obtainable] and/or normal serological results [when appropriate]).

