20.7.1.2 Recurrence and Survival

Secondary efficacy assessments will include recurrence (after EoT) and survival.

Survival: Survival will be determined on Day 42 and Day 84 (42 and 84 days after Screening/Treatment Day 1 [first dose of study drug]). This can be an in-person visit or a phone contact, and will document subject status only (alive or deceased). If subject is deceased, the relationship to the fungal infection will be recorded.

Recurrence: Recurrence will be assessed by measuring recurrence of the baseline fungal infection 42 days after EoT (Week 6 FU).

Recurrence is defined as global success at EoT but re-emergence of the baseline *Candida auris* infection during the post treatment follow-up. Re-emergence of the *Candida auris* infection is required to be with the same species and involving the same site that was initially identified at Screening/Treatment Day 1.

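### Global success requires a mycological response, but no culture is scheduled at EoT or Week 6 and no rule says how a subject without one is scored

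*Protocol*

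**What the plan says.** Protocol Section 11.1 defines the primary endpoint: "Efficacy as measured by the percentage of subjects with global success (complete or partial global response) at EoT as determined by the DMC". The committee is called the DMC in the protocol and the DRC in the SAP. Under Protocol 20.7.1.1, repeated in SAP 7.1, a complete or partial global response needs a clinical response "and a mycological response (mycological clearance (direct and/or negative cultures [when obtainable] and/or normal serological results [when appropriate".

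Protocol 16.10 calls for two sets of blood cultures on Day 1, repeated every day or two until they have stayed negative for 48 hours. After that, "Follow-up cultures will be performed as clinically indicated". For non-blood disease, a positive *C. auris* culture from the previous 7 days must be on hand at Day 1. Follow-up cultures in non-blood "infections should be performed as clinically indicated".

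The other laboratory and imaging evidence is scheduled more firmly at EoT. Table 1 marks serology there without qualification. Where outcome rests on imaging, Section 16.11 says "imaging scans must be available at Screening/Treatment Day 1 (prior to study treatment) and performed at EoT".

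Recurrence (Protocol 20.7.1.2, SAP 7.2) requires global success at EoT and then re-emergence, and the re-emerging "infection is required to be with the same species and involving the same site that was initially identified at Screening/Treatment Day 1".

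**The concern.** If culture after blood clearance is taken only when the clinical picture calls for it, whether a subject is cultured depends on how that subject is doing. A subject who is not improving is likely to be cultured; a subject whose wound, urinary or intra-abdominal infection looks better gives the site little reason to do so. Under Protocol 20.7.1.1, persistence on culture is one route to progressive disease, and that route is open only to subjects who were cultured. The same holds at Week 6, because naming the species and site of a re-emerging infection in practice takes a culture.

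The study has a single open-label arm, and Protocol 12.1 sets its results against historical standard-of-care subjects. No concurrent arm shares the same pattern of culturing. The planned display of global response by site of infection (SAP 7.3.1) would also compare candidemia, where clearance cultures are mandated, with sites where no follow-up culture is.

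**Working it through.** The documents give no figure to reproduce, because the planned 30 subjects rest on no formal calculation. The check is of the schedule against the definitions, followed by illustrations under stated assumptions.

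**1. Schedule (Table 1, the same in both documents).**

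| Outcome test | Visit 1 | EoT | Week 6 |
|---|---|---|---|
| Targeted examination | scheduled | scheduled | scheduled |
| Serology | scheduled | scheduled | if applicable |
| Imaging (row itself labelled as applicable) | scheduled | scheduled | if applicable |
| Mycological testing | scheduled | if applicable | if applicable |

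Culture is the only one of the four scheduled at neither EoT nor Week 6. At EoT it stands alone in this; at Week 6 imaging and serology are also if-applicable.

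**2. What is required after baseline.** For candidemia, blood cultures until clearance, then nothing fixed. For non-blood sites, no post-baseline culture of the site at any visit.

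**3. Timing.** Treatment can last 90 days (Protocol 14.1). If blood clearance were shown by Day 10 (an assumption; it is the end of the Days 7–10 visit window), the last mandated culture would precede a Day 90 EoT by 90 − 10 = 80 days, and the Week 6 visit by 80 + 42 = 122 days.

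**4. Scoring rules.**
- Protocol 20.4: a subject with no EoT assessment is a failure.
- SAP 7.1 and 7.1.1: an outcome that cannot be assessed because data are missing is not evaluable and is left out.
- Protocol 20.7.1.1: clearance may rest on "direct and/or negative cultures [when obtainable] and/or normal serological results [when appropriate".

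None of these addresses a subject who has an EoT or Week 6 assessment but no culture. The third allows success without an EoT culture; the second might exclude the same subject.

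**5. Illustration for the primary endpoint (all inputs assumed).** Take 24 of 30 subjects as clinical responders, 5–20% of them still culture-positive at EoT, and 25–75% of those not cultured. Wrongly scored successes = responders × proportion positive × proportion not cultured.
- Low: 24 × 0.05 × 0.25 = 0.3 subjects; 0.3 / 30 = 1 point.
- High: 24 × 0.20 × 0.75 = 3.6 subjects; 3.6 / 30 = 12 points.

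This treats every uncultured persistent infection as a success. The high end needs both worst-case proportions at once.

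**6. How far the scoring rule alone can move the result (counts assumed).** Start from 21/30 = 70.0% (95% Clopper-Pearson 50.6–85.3).

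| Successes without culture | Counted as failures | Excluded as not evaluable |
|---|---|---|
| 3 | 18/30 = 60.0% (40.6–77.3) | 18/27 = 66.7% (46.0–83.5) |
| 6 | 15/30 = 50.0% (31.3–68.7) | 15/24 = 62.5% (40.6–81.2) |
| 9 | 12/30 = 40.0% (22.7–59.4) | 12/21 = 57.1% (34.0–78.2) |

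This is not an estimate of bias. It shows how much depends on a rule that has not been written.

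**7. Recurrence (assumed).** Let true recurrence be 15%, let an uncultured recurrence never be counted, and let culturing be unrelated to recurrence. Observed recurrence = 15% × proportion cultured: 11.3%, 7.5% and 3.8% when 75%, 50% and 25% are cultured. Re-emergence with signs would prompt a culture, so the shortfall should be smaller and fall mainly on re-emergence without signs.

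**The case against.** The strongest reply is that the composite keeps laboratory evidence without a culture. β-glucan is scheduled at EoT and is otherwise repeated every 72 hours until negative (Protocol 16.12). Normal serology is a stated route to mycological response, and unchanged or worsened serology appears in the definitions of stable and progressive disease. The committee, not the treating investigator, determines the primary outcome. This stands, and it rules out one inference a reader might draw: that the composite collapses to open-label clinical judgement. It leaves two limits. Serology counts only where appropriate and is joined to culture by and/or. And β-glucan, described in Protocol 9.1 as a fungal cell-wall polymer, identifies neither the species nor the site that recurrence requires.

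A reader might also infer that missing cultures count as successes. The documents do not say so. The SAP's not-evaluable category could take such subjects, although nothing ties it to a missing culture. The defect is silence, not a rule that favours success.

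Nor do the documents support reading the plan as asking for no culture at all. Candidemia has mandated cultures to clearance, and non-blood disease must be culture-proven within 7 days of entry.

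On recurrence, the targeted examination at Week 6 is compulsory, so re-emergence with signs should lead to a culture. That also stands.

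Finally, making culture compulsory everywhere has a cost of its own. Under Protocol 20.7.1.1 persistence on culture is by itself progressive disease. A positive urine, wound, drain or sputum culture in an improved subject would become a failure, with no rule separating it from active infection. That limits the remedy, not the finding.

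**Conclusion.** The point holds. A required half of the primary endpoint has no scheduled culture at the visit where it is judged, and the secondary recurrence endpoint has none at Week 6. For candidemia the gap is the interval after clearance, which can be weeks. For non-blood sites it covers the whole post-baseline period. Neither document says how to score a subject assessed without a culture.

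The likely direction favours the drug, because culturing follows clinical status. The size cannot be had from the documents. The 1 to 12 points rest wholly on assumed inputs and are an upper-side illustration, since EoT serology or a not-evaluable ruling may catch some cases. What can be said firmly is that, as planned, the report would not show how much of the success rate rests on culture.

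**What to change.** 1. **SAP 7.1 (global response table) and the DRC form.** Record each mycological response as documented by a negative culture in the EoT window, supported by serology only, or presumed (neither). State the window in advance; Table 1 already gives EoT ±2 days. Report primary global success overall and, as a sensitivity analysis, with only culture-documented responses counted as success. Read the second figure as a conservative one, since a candidemia subject with proven earlier clearance but no culture in the window would not count.

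2. **SAP 7.2.** Report Week 6 recurrence together with the number of subjects actually cultured.

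3. **Protocol 16.10 and Table 1, for any subjects still to reach these visits.** Schedule a blood culture at EoT and at Week 6 for subjects with baseline candidemia. The SAP cites 2023 coding dictionaries, so this may reach few subjects; items 1 and 2 do not depend on it.

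Culture of non-sterile sites in improved subjects should not be made compulsory unless the DRC first has a rule for telling a positive culture without signs from active infection.

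The cost is one DRC field, one or two table rows, up to two blood cultures per candidemia subject (the EoT sample can be taken with the blood already drawn for safety tests and serology), a short amendment for item 3, and a possibly lower reported success rate.
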